9.1.10 Pharmacokinetic Analyses

The plasma concentration/time curves of CLB, N-CLB, CBD, CBD major metabolites, THC and THC major metabolites will be assessed at Visit 2 (Day 1 and Day 2) and Visit 4 (Day 33 and Day 34). Patients will be given their daily dose of clobazam at a scheduled time during Visit 2 and Visit 4 and the GWP42003-P/placebo immediately afterwards (Visit 4 only) to facilitate the accurate timing of blood samples required for PK analysis. Blood samples will be taken by either direct venipuncture or an indwelling cannula inserted into a forearm vein at the following times: Pre-dose and, 15 minutes, 30 minutes, 1 hour, 1.5 hours, 2 hours, 4 hours, 6 hours, 12 hours and 24 hours after dosing. The timing of each PK sample will be relative to the morning dose of CLB.

The pre-dose blood sample will be taken within 30 minutes prior to dosing. The allowable window for post-dose blood sample collection is ± 2 minutes up to and including 1 hour post-dose, ± 5 minutes from 1.5 hours up to and including 6 hours post-dose and ± 1 hour at 12 hours and 24 hours post-dose.

In the event of an AE that, in the opinion of the investigator, is related to a concomitant AED, additional blood samples may be collected.

Analysis of all PK samples will be conducted at a central clinical laboratory. Sample volume requirements and processing procedures will be detailed in a separate laboratory manual.

9.1.11 Genetic Testing

Genetic testing will only be conducted if specific consent is obtained from the participant. There is a separate informed consent form for this.

Genetic testing will be conducted to look at the CYP450 genes, with particular focus on CYP 2C19 and CYP 3A4, involved in the metabolism of AEDs and GWP42003-P.

9.1.12 Columbia Suicide Severity Rating Scale

The C-SSRS is to be completed by the investigator or his/her qualified designee at all hospital visits. Qualified designee is defined as physician, osteopath, nurse practitioner, clinical psychologist or physician's assistant who is licensed and has completed the C-SSRS training within the last two years. It is a brief standardized measure that uniquely assesses the essential information (behavior, ideation, lethality and severity) and distinguishes between suicidal occurrences and non-suicidal self-injury. The survey should be completed by the same assessor, where possible, throughout the study.

If the investigator or his/her qualified designee feel that the patient is either unable to answer the questions presented in C-SSRS, or that the questions are causing undue stress to the patient, the questionnaire may be skipped and this must be documented in the patient notes.

9.1.13 Patient Diary

Patients or their caregivers will be instructed on how to complete a paper diary and will be asked to record information daily in it. The number and type of seizures as well as information on AEs, concomitant AEDs and rescue medication will be collected each day from screening (Visit 1) until completion of dosing or withdrawal. Information on IMP intake will also be recorded each day from enrollment (Visit 2) until completion of dosing or withdrawal.

9.1.14 Investigational Medicinal Product Accountability

GWP42003-P/placebo will be dispensed at each of the following visits during the blinded phase:

- Visit 2 (Day 2)
- Visit 4 (Day 34)

IMP will be dispensed at each of the following visits for patients entering the OLE:

- Visit 5 (Two weeks)
- Visit 6 (One month)
- Visit 7 (Two months)
- Visit 8 (Three months)
- Visit 9 (Six months)
- Visit 10 (Nine months)
- Visit 11 (12 months)

Patients will be asked to return all IMP (used and unused) to each relevant visit (Visits 2 to 12). The site will check the returned IMP against the usage recorded in the paper diary. Any discrepancies will be discussed with the patient/caregiver and documented accordingly within the patient's source documents.

9.1.15 Adverse Events

Any adverse changes in the patient's medical condition, following completion of the consent form by the patient, will be recorded on the CRF as AEs, questioning the patient further if necessary. All AEs* occurring during the study, whether or not attributed to the IMP, observed by the investigator or reported by the patient will be recorded in the CRF.

* For the patient's expected seizure types, these do not routinely require documentation as AEs. However, any worsening, including change in the pattern or severity of seizures, must be documented as an AE.

Serious Adverse Events (SAEs) must be reported to GW Pharmacovigilance Department (PWD) within 24 hours of discovery or notification of the event, and recorded in the CRF.

Refer to [Section 12](#) for definitions, procedures and further information.

Inpatient hospitalizations that are, in the investigator's opinion, due to epilepsy will be recorded in the patient's CRF and through the SAE reporting process.

Refer to [Section 9.1.16.1.1](#) for the list of 'Triggering AEs of Interest' associated with monitoring of drug abuse liability.

9.1.16 Monitoring of Drug Abuse Liability

There are two triggers that will require the investigator or study coordinator to discuss abuse potential signals with the patient or their caregiver. These are either AEs of interest that may be reported by the patient/caregiver, or drug accountability issues regarding overuse of the IMP or missing bottles. Different questionnaires will be completed by the site depending upon which trigger occurs (see [Figure 9-1](#)).

Irrespective of the above, all patients/caregivers will be interviewed at their final dosing visit (Visit 5 or Visit 12) or withdrawal visit and a Study Medication Use and Behavior Survey will be completed by the investigator or study coordinator.

Investigators and study coordinators will be provided with training on how to complete and perform the processes outlined in this section. This training must be completed and documented by the relevant site staff prior to implementation at site.

9.1.16.1 Monitoring of Adverse Events

AE information will be collected according to [Section 9.1.15](#).

9.1.16.1.1 List of 'Triggering Adverse Events of Interest'

During the collection of AEs, if the patient reports an AE consistent with any of the following categories, then the investigator or study coordinator is required to complete an additional Supplemental Adverse Event Form and a Site Classification Form (investigator only) following further discussion of the event(s) with the patient or their caregiver. The categories are:

- Euphoria or inappropriate elation.
- Inappropriate laughter or exhilaration.
- Mood changes.
- Drunk, high or intoxicated.
- Hallucinations (visual or auditory), dissociations, disorientation, agitation.
- Disturbance in cognition, memory, or attention.
- Drug abuse.
- Drug withdrawal or drug withdrawal syndrome.
- Addiction.
- Overdose.
- Misuse of IMP.
- Thoughts of suicide, attempted suicide or suicide.

An AE that is consistent with the above categories will be known as a 'triggering AE of interest' for the purposes of this study.

9.1.16.1.2 Supplemental Adverse Event Form

This form consists of 15 questions regarding the AE and use of IMP. It is completed as part of an interview with the patient/caregiver when a triggering AE of interest is reported. It is important that this is completed by a trained investigator or study coordinator with the patient/caregiver present. The answers on the Supplemental Adverse Event Form will then be transcribed into the patient's CRF for the study. If the Supplemental Adverse Event Form cannot be completed at the time the triggering AE of interest is reported, then the site should contact the patient/caregiver to obtain the required answers as soon as possible.

9.1.16.2 Monitoring Drug Accountability Discrepancies

Any time after enrollment until final collection of study data, drug accountability discrepancies are monitored as follows:

- At routine Drug Accountability collection times, the site personnel will collect the IMP clinical supplies and make sure the usage is in line with the expectations reported within the paper diary.
- At any time that the site is informed by the patient/caregiver about any overuse of IMP, suspected misuse, abuse, or diversion.

9.1.16.2.1 List of 'Triggering Drug Accountability Discrepancies'

If there are any discrepancies in drug accountability as outlined by the criteria below, known as 'triggering drug accountability discrepancies', then the trained investigator or study coordinator will complete a Supplemental Drug Accountability Form and Site Classification Form (investigator only) following further discussion of the event(s) with the patient/caregiver. The triggering drug accountability discrepancies are as follows:

- Missing bottle(s).
- Compliance issues where one or more bottles are used compared to what was the expected use, according to the paper diary.
- Returned IMP supply with evidence of tampering.
- Greater than the target daily dose as recorded in the paper diary.

9.1.16.2.2 Supplemental Drug Accountability Form

This form consists of eight questions regarding various aspects of drug accountability and patient usage. It is completed as part of an interview with the patient/caregiver when a triggering drug accountability discrepancy is identified. It is important that this is completed by a trained investigator or study coordinator with the patient/caregiver present. The answers on the Supplemental Drug Accountability Form will then be transcribed into the patient's CRF for the study. The accountability reporting procedures will still occur. If the Supplemental Drug Accountability Form cannot be completed at the time the triggering drug accountability discrepancy is identified, then the site should contact the patient/caregiver by telephone to obtain the required answers as soon as possible (Note: IMP refers to GWP42003-P or placebo, not other concomitant medications).

9.1.16.3 Site Classification Form

The investigator should review the applicable Supplemental Adverse Event Form or Supplemental Drug Accountability Form, and then complete the Site Classification Form. For each Supplemental Adverse Event Form or Supplemental Drug Accountability Form completed, there should be an associated Site Classification Form.

The Site Classification Form requires the investigator to assign the finding to an appropriate classification and then to also assign the possible relationship to the IMP. The investigator is also required to indicate the level of the certainty of the classification. The answers from the Site Classification Form will then be transcribed into the patient's CRF for the study.

9.1.16.4 Study Medication Use and Behavior Survey

This form consists of 18 questions regarding the use of the IMP. The trained investigator or study coordinator will complete this survey as an interview with the patient/caregiver at the final dosing visit (Visit 5 or Visit 12) or withdrawal visit. The answers on the Study Medication Use and Behavior Survey will then be transcribed into the patient's CRF for the study.

The Study Medication Use and Behavior Survey will be completed for all patients in the study and not only those that have reported a triggering AE or drug accountability discrepancy.

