4.1.2 Secondary Endpoint(s)

To assess the safety and tolerability of GWP42003-P compared with placebo when taken in combination with CLB. Safety and tolerability will be assessed using the following parameters:

- AEs
- 12-lead Electrocardiogram (ECG)
- Clinical laboratory parameters (clinical chemistry, hematology and urinalysis)
- Vital signs
- Columbia-Suicide Severity Rating Scale (C-SSRS)
- Seizure Frequency
- Abuse Liability

PK parameters (C_{max} , t_{max} , $AUC_{(0-\infty)}$, $AUC_{(0-t)}$, $t_{1/2}$) of the following analytes:

- THC
- THC major metabolites

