8.1.2 Dose Escalation and Dose Adjustments

Patients will enter the blinded phase of the study and will be up-titrated over ten days (Day 2 to Day 11) to a maintenance dose or equivalent of GWP42003-P/placebo of 20 mg/kg/day. If GWP42003-P is not tolerated then the dose can be reduced accordingly at the discretion of the investigator. The titration regimen is described in [Table 8.1.2-1](#).

Table 8.1.2-1 Dose Up-Titration Regimen*		
Day - GWP42003-P/Placebo (Blinded Period)	Day - GWP42003-P only (OLE**)	Dose Level (GWP42003-P or equivalent placebo)
2	34	2.5 mg/kg
3	35	2.5 mg/kg
4	36	5.0 mg/kg
5	37	5.0 mg/kg
6	38	7.5 mg/kg
7	39	7.5 mg/kg
8	40	10.0 mg/kg
9	41	10.0 mg/kg
10	42	15.0 mg/kg
11	43	15.0 mg/kg
12 onwards	44 onwards	20.0 mg/kg

*GWP42003-P /placebo is to be taken twice daily. Total daily doses are shown.

** Only patients who were taking placebo during the double-blind period will up-titrate according to this schedule during the OLE period. Those taking GWP42003-P during the double-blind period will down-titrate their blinded IMP whilst simultaneously up-titrating with GWP42003-P, thus maintaining a daily dose of 20 mg/kg/day GWP42003-P throughout.

The titration regimen defined above should be followed to the maximum dose (20 mg/kg/day). Should an AE occur during titration which is attributable to IMP or concomitant AED, then IMP dose should be reduced to the next lower dose. Any other changes in concomitant AED therapy should be reviewed with the medical monitor before being initiated.

For those patients who do not enter the OLE the dose of GWP42003-P/placebo will taper off over 10 days beginning on Day 34. The patient will reduce the dose by 10% of the maintenance dose each day and treatment will end on Day 43.

Patients who enter the OLE period will be transitioned to the OLE treatment over a 10-day period in order to maintain blinding, simultaneously down-titrating blinded GWP42003-P /placebo whilst up-titrating open-label GWP42003-P. As such, patients who were taking GWP42003-P during the blinded period will maintain their 20 mg/kg/day dose throughout the transition from the blinded period into the OLE period and patients who received placebo during the blinded period up-titrate slowly to the 20 mg/kg/day dose in the OLE period. After this has taken place, the

maintenance dose of GWP42003-P may be adjusted up or down at the discretion of the investigator to a maximum of 30 mg/kg/day (no minimum).

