9.2.1.4.2 Visit 4 (Day 34)

This is the second part of the two day visit. The final PK sample will be collected 24 hours after the Day 33 morning CLB dose.

Following completion of the PK sampling process the following observations will be made on Day 34: concomitant medications (including AEDs), physical examination (including body weight), vital signs and AEs.

At the end of the blinded phase of the study on Day 34, providing the investigator and patient both agree, patients will be invited to continue taking GWP42003-P and to enter the OLE.

Patients who enter the OLE will be dispensed GWP42003-P on Day 34. At the point of entry to the OLE, patients will be transitioned to the OLE treatment over a 10 day period in order to maintain blinding. The dose may be adjusted up or down by the investigator from the maintenance dose of 20 mg/kg/day in the blinded phase to a maximum of 30 mg/kg/day in the OLE. Patients and/or their caregivers will be provided with individual dosing schedules as described in [Section 8.1.2](#). Patients, or their caregivers, will be instructed how to record the diary information.

Patients who do not enter the OLE will begin a 10 day taper period during which they will taper off their daily dose of GWP42003-P/placebo. The daily dose will be reduced by 10% of the maintenance dose per day and treatment will end on Day 42.

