9.2.1.5 Visit 5 (Patients not entering Open Label Extension) (Day 43 +3 days)

This visit will occur 42 days after Visit 2, Day 1 (enrollment) for those patients who do not enter the OLE.

All GWP42003-P/placebo (used and unused) will be collected and a check of the returned GWP42003-P/placebo against usage must be made. A physical examination (including body weight), ECG and vital signs will be assessed and the C-SSRS will be administered. The trained investigator or study coordinator will complete the Study Medication Use and Behavior Survey as an interview with the patient/caregiver. Clinical laboratory samples (blood and urine) will be taken for hematology, biochemistry and urinalysis and a review of concomitant medications (including AEDs) and AEs will be completed. Patient diaries will be collected.

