9.2.2.8 Visit 12 (Open Label Extension End of Taper)

This visit will be ten days after Visit 11. All IMP (used and unused) will be collected and a check of the returned IMP against usage must be made. A physical examination (including body weight), ECG and vital signs will be assessed and the C-SSRS will be administered. The trained investigator or study coordinator will complete the Study Medication Use and Behavior Survey as an interview with the patient/caregiver.

Clinical laboratory samples (blood and urine) will be taken for hematology, biochemistry and urinalysis and a review of concomitant medications (including AEDs) and AEs will be completed. Patient diaries will be collected and reviewed.

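### The abuse-liability survey is not given at the end of the blinded phase, so its placebo data come only from the few placebo patients who decline the open-label extension or withdraw early

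*Protocol*

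**What the plan says.** Section 4.1.2 lists abuse liability among the safety and tolerability parameters, under the aim "To assess the safety and tolerability of GWP42003-P compared with placebo when taken" in combination with clobazam.

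Section 9.1.16 describes three sources of abuse-liability information. Two are triggers: adverse events of interest and drug-accountability discrepancies. The third is an 18-question survey given to every patient whether or not a trigger has occurred. Sections 9.1.16 and 9.1.16.4 give it the same timing: an interview with the "patient/caregiver at the final dosing visit (Visit 5 or Visit 12) or withdrawal visit".

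The visit sections settle who is surveyed when:
- **Visit 4 (sections 9.2.1.4.1 and 9.2.1.4.2):** no survey. The Day 34 observations are "concomitant medications (including AEDs), physical examination (including body weight), vital signs and AEs".
- **Visit 5 (section 9.2.1.5):** "This visit will occur 42 days after Visit 2, Day 1 (enrollment) for those patients who do not enter the OLE". The survey is done here.
- **OLE visit also numbered 5 (section 9.2.2.1):** no survey.
- **Visit 12 (section 9.2.2.8):** "This visit will be ten days after Visit 11", which is itself the twelve-month OLE visit. The survey is done here.

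The Version 2 schedules reproduced in Amendment 1, Appendix 1.4, agree with this.

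On OLE entry, section 8.1.2 moves everyone to open-label drug: "period and patients who received placebo during the blinded period up-titrate slowly" to 20 mg/kg/day, starting on Day 34.

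**The concern.** A comparison with placebo needs observations made while the randomized arms still differ. For a patient who enters the OLE, Visit 4 is the last such contact, and the patient is still blinded then. Adverse events, laboratory tests, ECG, vital signs and the C-SSRS are all collected at Visit 4; the survey is not.

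A former placebo patient who enters the OLE is therefore first surveyed after taking active drug. A former GWP42003-P patient is surveyed after both blinded and open-label use. The only surveys from patients exposed to placebo alone come from those who decline the OLE or withdraw during the blinded phase. That group is chosen by decisions made after randomization.

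The section 13.2 interim analysis at the end of the double-blind phase would have no survey from any OLE entrant. Surveys not taken at that point cannot be recovered by any later analysis.

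**Working it through.** The protocol states no figure for this endpoint (section 13.1 has no formal sample size), so there is none to reproduce.

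**Inputs**
- Total patients: 20 (section 13.1).
- Allocation: 4:1, GWP42003-P to placebo (section 7.2).
- OLE drug starts on Day 34 (section 8.1.2); the OLE lasts at most one year (section 4.1); Visit 12 is ten days after the twelve-month Visit 11 (section 9.2.2.8).
- OLE uptake p: not stated, so assumed and varied.

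**Step 1: arm sizes.** Placebo: 20 × 1/5 = 4. GWP42003-P: 20 × 4/5 = 16.

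**Step 2: first survey of a placebo patient who completes a full OLE.** 34 + 365 + 10 = about Day 409. Earlier withdrawal from the OLE brings the survey forward, but it still follows open-label drug.

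**Step 3: surveys reflecting randomized treatment alone.** Assume no blinded-phase withdrawals, the same uptake in both arms and independent decisions. The expected number is then 4(1-p) on placebo and 16(1-p) on GWP42003-P. The chance of no placebo-only survey is p^4.

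| Assumed uptake p | Placebo, 4(1-p) | GWP42003-P, 16(1-p) | Chance of no placebo-only survey, p^4 |
|---|---|---|---|
| 0.50 | 2.0 | 8.0 | 6% |
| 0.75 | 1.0 | 4.0 | 32% |
| 0.80 | 0.8 | 3.2 | 41% |
| 0.90 | 0.4 | 1.6 | 66% |

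**Step 4: with a survey at Visit 4.** Every patient still in the study contributes: up to 4 on placebo and 16 on GWP42003-P, whatever the OLE uptake.

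**The case against.** A reader might infer that the placebo comparison for abuse liability as a whole is lost. The documents do not support that. Adverse events are collected from Visit 1, and accountability is monitored from enrollment, in both arms. Each trigger leads to a supplemental form and a site classification, and triggered cases go to adjudication (sections 9.1.16.1 to 9.1.16.5). Those components keep their blinded-phase comparison.

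Nor can it be said that the survey supports no statement against placebo. Placebo patients who decline the OLE are surveyed at Visit 5, and those who withdraw in the blinded phase are surveyed at withdrawal. At an uptake of 0.5, two placebo-only surveys are expected, and the chance of at least one is 94%.

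Three further points deserve weight:
- **The timing has a rationale.** An exit interview after the taper can pick up withdrawal phenomena, and drug withdrawal is one of the triggering categories in section 9.1.16.1.1. This is a reason to keep the later surveys. It is not a reason to omit one at Visit 4.
- **The questions are not shown.** The interview might ask separately about blinded and open-label use. Even so, a former placebo patient would be recalling the blinded phase up to a year later, after open-label treatment.
- **The gain is small.** The analysis is descriptive. If 0 of 4 placebo patients reported a finding, the one-sided 95% upper limit would still be 1 - 0.05^(1/4) = 53%. This limits the importance of the point. But with only about four controls, each one missed is a large share of the control data.

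**Conclusion.** The point holds for the survey component only. The protocol schedules no survey at the end of the blinded phase, and placebo patients who enter the OLE are first surveyed after GWP42003-P. The survey's placebo data therefore come from a self-selected subset of about 4 patients and may be empty: a 6% chance at an assumed OLE uptake of 0.5, rising to 66% at 0.9.

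The timing gap is plain from the text. Its size is conditional on the assumed uptake, on no blinded-phase withdrawals and on independent decisions. The rest of the abuse-liability endpoint is unaffected. This is a worthwhile, inexpensive improvement of modest value.

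**What to change.** In sections 9.1.16, 9.1.16.4 and 9.2.1.4.2 and in the Appendix 1 schedule, add a Study Medication Use and Behavior Survey for every patient at Visit 4 (Day 34), completed before any open-label dose. Keep the existing Visit 5, Visit 12 and withdrawal administrations. State that the Visit 4 survey is used for the descriptive comparison with placebo and that Visit 12 is reported as uncontrolled OLE data.

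The cost is one extra 18-question interview for each of at most 20 patients, at an existing visit and by staff already trained in it, plus schedule and case report form wording. The Day 34 visit becomes slightly longer. With at most about 4 placebo patients, the comparison remains descriptive.
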